2.2 Secondary Objectives

Analytical sub-aims of the protocol are to: 1) Describe characteristics of women who under-attend for cervical cancer screening in a safety net health system; 2) Explore patterns of detection and treatment of cervical pre-cancers across study arms; 3) Compare characteristics of screening participants across study arms.

We will also conduct a nested study within the randomized controlled trial to assess acceptability of and experiences with self-sample HPV testing among underscreened women in our safety net health system. The nested study has two components: a telephone survey and in-depth

qualitative interviews. In the remainder of the protocol these will be referred to as "Telephone Survey" and "Qualitative Interviews."

Because of the COVID-19 pandemic, we have revised some elements of the trial, as reflected throughout the protocol. One of these revisions includes expansion of analytic sub-aim 1 (above) to include monitoring of ambulatory, and more specifically, primary care utilization in addition to cervical cancer screening. The COVID-19 era sub-aims are: 1) To compare changes in cervical cancer screening and primary care utilization (overall and by face-to-face vs. telehealth modalities) among socioeconomic, racial/ethnic, and nativity subgroups in the 12-months following the COVID-19 emergency declaration; and 2) To compare the role of individual and neighborhood-level factors on cervical cancer screening and primary care utilization (overall and modality-specific) before and after the COVID-19 emergency declaration. In the remainder to the protocol, we will refer to COVID-19 era analytic sub-aims.

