cancers worldwide) to improve risk stratification and determine the appropriate algorithm for clinical follow-up. As is standard, test results will be interpreted as 1) HR-HPV negative, 2) HR-HPV positive and HPV 16/18/45 negative; 3) HR-HPV positive and HPV 16/18/45 positive; or 4) inadequate (due to unsatisfactory sample). Kits that are returned after >30 days will also be considered inadequate.

Test results will be sent via Harris Health secure transmission to co-investigator [name], the study coordinator, and the PN team. Notification of test results and referral for clinical follow-up: HR-HPV positive test results will be communicated on a weekly basis to co-investigator [name]. [name] will be responsible for referring HR-HPV positive women to clinical follow-up. Notification to participants of both negative and positive results will be conducted by the PNs, who will contact participants by telephone within 10 days of the laboratory's receipt of the sample. Participants who are unreachable after 3 telephone attempts on different days/times will be mailed their results by certified mail. Results will be reported as follows: HR-HPV negative women will be told that no high-risk HPV strains were found in their sample. However, since self-sampling is not currently approved for primary screening, women will be advised to attend for clinic-based screening within the next 12 months. [name] is now affiliated with MD Anderson and will continue to provide clinical oversight for the trial and review lab results through the secure Harris Health EMR system. MD Anderson has been added as a site for this study with the BCM IRB. HR-HPV positive. Women who test positive for HR-HPV but negative for 16/18/45 will be referred by [name] to clinic-based screening (Pap/HR-HPV co-testing). They will be asked to make an appointment with their healthcare provider and given clinic contact information. Women who test positive for HR 16/18 will be referred to colposcopy. As is standard practice at Harris Health when screening abnormalities are encountered, women requiring follow-up Pap test screening or colposcopy who have not made an appointment within 30 days of test result notification will receive a telephone call from a PN who will assist them with scheduling an appointment.

Inadequate: Women whose samples were inadequate (due to unsatisfactory sampling or kit returned after >30 days) will be advised to attend for clinic-based screening or mailed a new kit.

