Ascertainment of Outcomes Primary outcome. The primary outcome is primary screening participation, defined as completion and return of a mailed self-sample HPV testing kit that is tested in the lab or attendance for clinic-based screening within 6 months of randomization. Receipt of mailed self-sample HPV testing kits will be ascertained by reviewing lab records. Attendance for clinic-based screening will be ascertained by the study coordinator based on review of the Harris Health EMR. Primary screening participation will be dichotomously categorized as screened/unscreened. Secondary outcomes are screening tests results (positive, negative, or inadequate) and completion of clinical follow-up among women with an abnormal screening test result (attended, did not attend). Screening test results will be ascertained within 6 months of randomization. Pap/HR-HPV co-testing results will be ascertained by EMR review. Self-sample HR-HPV test results will be based on laboratory reports. Completion of clinical follow-up will be ascertained by EMR review within 6 months of the date of the screening test result. Completion of clinical follow-up is defined as attendance for colposcopy among participants who had a positive test by clinic-based screening and attendance for colposcopy or subsequent clinic-based screening among those who had a positive test by self-sampling. Additional exploratory outcomes (sub-aim 2) are detection and treatment of cervical precancers (i.e., histologically-confirmed cervical intraepithelial neoplasia grade II or greater [CIN2+]). Precancers will be ascertained by EMR review within 6 months of abnormal screening results and treatment as per ASCCP guidelines will be ascertained within 6 months of the date of diagnosis. Completion of primary care appointments will be ascertained at 6 months, including telehealth appointments. Additional variables will be collected to meet the aims of the NIH-funded supplement (3R01MD013715-04S1) to the parent trial: HIV status, Preventive Care Gap Score, Enrollment in MyHealth portal, History of COVID-19 diagnosis, HPV vaccination status and Risk of Admission or ED visit. We will also collect Mental and Behavioral Disorders due to use of the following: alcohol (Code F10), opioids (Code F11), cannabis (Code F12), sedatives, hypnotics, anxiolytics (Code F13), cocaine (Code F14), other stimulants, including caffeine (Code F15),

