3.4 Data Analysis

Randomized Controlled Trial Primary outcome. Primary screening participation will be examined dichotomously (screened/not screened) using an "intent-to-screen" analytic approach. Bivariable tables and Pearson's χ^2 tests will be used to compare the proportion of primary screening participation across Arms 1, 2, and 3, as well as the absolute difference in participation across Arms 1, 2 and 3. Bivariable tables and Pearson's χ^2 tests will be used to compare the proportion of primary screening participation by study arm, as well as the absolute difference in participation across arms. Log binomial regression will be used to calculate the relative risks of primary screening participation and corresponding 95% confidence intervals (CIs). Secondary outcomes. Descriptive analyses of secondary outcomes will be conducted using bivariable tables and Fisher's exact tests to describe and compare test results and attendance for clinical follow-up across study arms 1, 2 and 3. Log binomial regression will be used to calculate relative risks and 95% CIs of having a positive screening test and of attending for clinical follow-up.

Analytic sub-aim: 1) We will use descriptive statistics (bivariable tables and chi-square/Fisher's exact tests) to compare characteristics of un/under-screened women and those who are up-to-date on screening across Arms 1, 2, and 3. Multivariable logistic regression will be used to assess the independent association between screening status and participant characteristics. 2) Detection and treatment of precancers will be explored through descriptive analyses using bivariable tables and Fisher's exact tests. 3) Among participants in Arms 1, 2 and 3, we will conduct separate analyses to assess characteristics associated with primary screening participation. For Arms 1, 2 and 3, we will use bivariable tables with Pearson's χ^2 tests to describe characteristics of screened and unscreened participants. Characteristics of interest include age, race/ethnicity, months since last Pap test, health plan type, number of healthcare encounters in the past 12 months, and time enrolled as a Harris Health patient. Associations with $p<0.10$ will be used to determine candidate variables for subsequent multivariable

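### The single 6-month CIN2+ window does not fit the two-step kit route found only in Arms 2 and 3, and the plan does not say which abnormal result starts the clock

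*Combined protocol and SAP*

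**What the plan says.** Section 2.2 lists as a sub-aim: "Explore patterns of detection and treatment of cervical pre-cancers across study arms". Section 3.1 gives its status: "Additional exploratory outcomes (sub-aim 2) are detection and treatment of cervical precancers", which must be histologically confirmed as CIN2+. The window is "Precancers will be ascertained by EMR review within 6 months of abnormal screening results", and treatment is then ascertained within 6 months of diagnosis. Section 6.1 repeats both rules. Section 3.4 adds: "Detection and treatment of precancers will be explored through descriptive analyses using bivariable tables", with Fisher's exact tests. It states no denominator for CIN2+.

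The route to histology depends on the test. For kits, Section 3.1 says "Women who test positive for HR-HPV but negative for 16/18/45 will be referred by [name] to clinic-based screening (Pap/HR-HPV co-testing"), whereas "Women who test positive for HR 16/18 will be referred to colposcopy". For a positive clinic-based screen, follow-up counts as complete at colposcopy. For a positive kit, a further clinic screen also completes it. Kit results are to be notified within 10 days of laboratory receipt, and women needing follow-up "who have not made an appointment within 30 days of test result notification will receive a telephone call from a PN".

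**The concern.** The completion rule for clinical follow-up recognises that some kit positives go to another clinic screen first. The CIN2+ rule makes no matching allowance. A kit-positive, 16/18/45-negative woman who attends her co-test in month 5 is recorded as having completed follow-up. If that co-test leads to colposcopy, the histology may arrive after the window closes, and she is then recorded as having no CIN2+.

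Only Arms 2 and 3 contain such women, so any loss is linked to arm and runs against the kits in the comparison that sub-aim 2 sets out. Treatment counts inherit it, because treatment is dated from diagnosis. Section 1.2 rests part of the trial's significance on early detection of precancer, so readers will look at this table even though it is exploratory.

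**Working it through.** The plan gives no CIN2+ rate, sample size or power, so there is no figure to reproduce. The check compares the routes, then the time each leaves.

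**Routes to histology**

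| Abnormal result | Steps described or implied | Arms |
|---|---|---|
| Clinic-based screen | colposcopy | 1, 2, 3 |
| Kit, HPV 16/18 positive | colposcopy | 2, 3 |
| Kit, HR-HPV positive, 16/18/45 negative | co-test, its result, then colposcopy if indicated | 2, 3 |

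Colposcopy after an abnormal co-test is inferred from the completion rule for clinic positives.

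**Window arithmetic, clock starting at the kit result**

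Inputs from Section 3.1: 6 months (taken as 183 days), up to 10 days to notification, and 30 days without an appointment before the navigator call. Assumed: 14 to 90 days to the co-test visit and 7 to 14 days for its result.

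- Direct to colposcopy: 183 − 10 = 173 days left. If the 30 days are also used, 173 − 30 = 143.
- Co-test first: from 183 − 10 − 14 − 7 = 152 down to 183 − 10 − 90 − 14 = 69 days left. If the 30 days are used once, 122 down to 39.

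The 10 days run from laboratory receipt, so part of them may precede the result. That does not alter the gap between the routes, which is 14 + 7 = 21 to 90 + 14 = 104 days.

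**Illustrative loss**

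Waits to the co-test (V) and to colposcopy (C) were simulated as gamma variables with shape 2 and means of 30, 60 or 90 days. Notification took 10 days and the co-test result 10 days.

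- d = P(10 + C ≤ 183), the share of CIN2+ caught on the direct route.
- t = P(10 + V + 10 + C ≤ 183), the share caught on the co-test route.
- s = share of kit positives that are 16/18/45 negative (0.50, 0.70 or 0.85).
- r = their CIN2+ risk relative to 16/18/45 positives (0.3, 0.5 or 1.0).
- c = s·r / (s·r + 1 − s), their share of CIN2+ among kit positives.
- Relative shortfall against an all-direct route = c × (1 − t/d).

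| Mean waits (V, C) | d | t | s | r | c | Shortfall |
|---|---|---|---|---|---|---|
| 30, 30 | 1.000 | 0.995 | 0.50 | 0.3 | 0.231 | 0.1% |
| 60, 60 | 0.979 | 0.792 | 0.70 | 0.5 | 0.538 | 10.3% |
| 90, 90 | 0.896 | 0.489 | 0.85 | 1.0 | 0.850 | 38.6% |

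The first and last rows are the extremes of all combinations run. None of V, C, s or r is in the documents.

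**Clock restarting at an abnormal co-test**

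The co-test may count as follow-up up to 6 months after the kit result, and CIN2+ could then be counted for 6 months more. That is 6 + 6 = about 12 months from the first abnormal result, against 6 for a clinic-screened woman. Ascertainment is again unequal, now in favour of the kit route.

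**The case against.** Several objections have force.

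- **The anchor is not stated.** Clinical follow-up is dated from a single test result, but the CIN2+ sentence speaks of abnormal results without naming the index test, and the protocol describes the co-test as clinic-based screening. An abnormal co-test could therefore restart the clock, which would remove most of the shortfall. This stands, but it replaces one inequality with the opposite one.
- **The Arm 1 route is partly inferred.** The colposcopy wording defines completed follow-up; it is not a referral rule for every clinic positive. Section 3.1 describes usual practice after abnormalities as including a follow-up Pap test. The documents do not prove that the clinic route is always one visit.
- **The outcome is exploratory.** It is analysed descriptively and appears in neither Hypothesis 1.1 nor 1.2.

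A reader might infer more than the documents support. That most kit positives take the longer route cannot be shown, because no genotype split is given and 16/18 positives go directly to colposcopy. Nor does the extra step apply to Arms 2 and 3 as a whole: women there who screen in clinic follow the same route as Arm 1.

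A reader might also stack the delays: 10 + 30 + 30 = 70 of about 182 days, leaving 112, or 56 per appointment wait, and conclude that 8-week waits miss the window. That spends every allowance in full and may count days before the result. Even so, 70 + 112 = 182, so exactly 8 weeks per wait still fits. That a true gain from kits would be reversed is unsupported, since no arm-level figure can be derived.

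**Conclusion.** The point holds as a possible, arm-linked inequality of ascertainment. It is not an established under-count. On the plain reading, where the kit result starts the clock, the bias can only lower CIN2+ in Arms 2 and 3 relative to Arm 1. On the restart reading, the kit route gets the longer window. The direction is known under each reading, and the plan does not choose between them. The size could be negligible or material: the 0.1% to 39% range applies to kit positives only and rests wholly on assumed waits, genotype share and relative risk. Screening participation and completion of clinical follow-up are unaffected. The change is worth making because it is cheap and the outcome is compared across arms, but it is not critical to the trial's main conclusions.

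**What to change.** In Sections 3.1 and 6.1, for women whose trial screen within 6 months of randomization was abnormal, ascertain CIN2+ to one common date, 12 months from randomization. In Section 3.4, compare arms with all randomized women as the denominator. Keep treatment at 6 months from diagnosis. No clinical procedure changes.

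The restriction to an abnormal trial screen is needed. Kit-negative women are advised to have a clinic screen within the next 12 months, and no such advice is described for clinic-negative women. Counting CIN2+ found that way would bias the comparison towards the kits. CIN2+ from later re-screening of women with a negative trial screen, or from first screens after month 6, should be excluded or reported separately.

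On the plain reading the present rules already run to 6 + 6 = 12 months from randomization, so no case now counted is lost and the last ascertainment date does not move. On the restart reading some later cases would no longer count. Section 4 plans completion at 36 months after 30 months of accrual. That leaves 6 months after the last enrolment, which already does not fit the 12-month rule (18 with treatment); the fix does not worsen this.

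The cost is a longer chart look-back for women screened early. One limit remains: a woman whose kit result comes near month 6 still has only about 6 months for two visits.

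Separately, Section 3.1 groups HPV 45 with 16 and 18 when reporting results but names only 16/18 in the colposcopy referral. Those statements must be reconciled so that each woman's route is defined.

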3.2 Questionnaires

1. **Telephone Survey:** Descriptive statistics will be used to identify experiences of self-sampling among survey participants who completed and returned a kit. The main effects of patient navigation on overall experience will be assessed using bivariable tables and Pearson's χ^2 or Fisher's exact tests. Associations with $p<0.05$ will be considered statistically significant. Additionally, we will explore patterns related to specific barriers in the scale using exploratory bivariable analyses. For those participants who did not return a kit, descriptive statistics will be used to describe barriers to clinic-based screening and reasons for using the self-sampling kit. Bivariable tables and Pearson's χ^2 or Fisher's exact tests will be used to explore differences in barriers to clinic-based screening between kit returners and non-returners.
2. **Qualitative Interview Guide:** The semi-structured interviews will be transcribed by a professional transcription service and kept in the language in which they were conducted (English or Spanish). The PI, who is bilingual in English and Spanish and experienced in qualitative data analysis, will conduct a close reading of the transcripts to develop a coding scheme. Once the coding scheme is developed, coding rules and procedures will be detailed in a codebook and described to two independent coders (the research coordinator and research assistant) who will classify the dataset. Cohen's Kappa coefficient [86] will be used to evaluate inter-coder reliability. Iterative content analysis will be used to collapse codes into emergent themes. A summative approach will be used to describe and compare codes and themes across women who do and do not attend for clinical follow-up.

3.3 Source Document and Case Report Forms

All source documentation is housed on Harris Health's electronic medical records system, Epic.

3.4 Data Analysis

Randomized Controlled Trial Primary outcome. Primary screening participation will be examined dichotomously (screened/not screened) using an "intent-to-screen" analytic approach. Bivariable tables and Pearson's χ^2 tests will be used to compare the proportion of primary screening participation across Arms 1, 2, and 3, as well as the absolute difference in participation across Arms 1, 2 and 3. Bivariable tables and Pearson's χ^2 tests will be used to compare the proportion of primary screening participation by study arm, as well as the absolute difference in participation across arms. Log binomial regression will be used to calculate the relative risks of primary screening participation and corresponding 95% confidence intervals (CIs). Secondary outcomes. Descriptive analyses of secondary outcomes will be conducted using bivariable tables and Fisher's exact tests to describe and compare test results and attendance for clinical follow-up across study arms 1, 2 and 3. Log binomial regression will be used to calculate relative risks and 95% CIs of having a positive screening test and of attending for clinical follow-up.

Analytic sub-aim: 1) We will use descriptive statistics (bivariable tables and chi-square/Fisher's exact tests) to compare characteristics of un/under-screened women and those who are up-to-date on screening across Arms 1, 2, and 3. Multivariable logistic regression will be used to assess the independent association between screening status and participant characteristics. 2) Detection and treatment of precancers will be explored through descriptive analyses using bivariable tables and Fisher's exact tests. 3) Among participants in Arms 1, 2 and 3, we will conduct separate analyses to assess characteristics associated with primary screening participation. For Arms 1, 2 and 3, we will use bivariable tables with Pearson's χ^2 tests to describe characteristics of screened and unscreened participants. Characteristics of interest include age, race/ethnicity, months since last Pap test, health plan type, number of healthcare encounters in the past 12 months, and time enrolled as a Harris Health patient. Associations with $p<0.10$ will be used to determine candidate variables for subsequent multivariable

models. Multivariable log binomial regression models will be built to assess the independent association between screening participation and participant characteristics after adjusting for relevant covariates. The likelihood ratio test will be used to examine the relative contribution of specific variables to the fit of the model. Adjusted risk ratios will be reported and will be considered statistically significant at $p<0.05$.

Telephone Survey Descriptive statistics will be used to identify experiences of self-sampling among survey participants who completed and returned a kit. The main effects of patient navigation on overall experience will be assessed using bivariable tables and Pearson's χ^2 or Fisher's exact tests. Associations with $p<0.05$ will be considered statistically significant. Additionally, we will explore patterns related to specific barriers in the scale using exploratory bivariable analyses. For those participants who did not return a kit, descriptive statistics will be used to describe barriers to clinic-based screening and reasons for using the self-sampling kit. Bivariable tables and Pearson's χ^2 or Fisher's exact tests will be used to explore differences in barriers to clinic-based screening between kit returners and non-returners.

Qualitative Interviews The semi-structured interviews will be transcribed by a professional transcription service and kept in the language in which they were conducted (English or Spanish). The PI, who is bilingual in English and Spanish and experienced in qualitative data analysis, will conduct a close reading of the transcripts to develop a coding scheme. Once the coding scheme is developed, coding rules and procedures will be detailed in a codebook and described to two independent coders (the research coordinator and research assistant) who will classify the dataset. Cohen's Kappa coefficient [86] will be used to evaluate inter-coder reliability. Iterative content analysis will be used to collapse codes into emergent themes. A summative approach will be used to describe and compare codes and themes across women who do and do not attend for clinical follow-up.

COVID-19 era analytic sub-aim: 1) We will use descriptive statistics (bivariable tables and chi-square/Fisher's exact tests) to compare characteristics of women who do/do not attend for cervical cancer screening, primary care (all types), and telehealth-specific primary care. We will compare proportions at baseline (February 2020, pre-pandemic), and at 6- and 12-months post COVID-19 emergency declaration (July 2020 and February 2021). Independent multivariable Poisson regression models will be used to assess the independent association between cervical cancer screening and primary care utilization and participant characteristics.

Additional variables will be collected to meet the aims of the NIH-funded supplement (3R01MD013715-04S1) to the parent self-sampling trial: HIV status, Preventive Care Gap Score, Enrollment in MyHealth portal, History of COVID-19 diagnosis, HPV vaccination status and Risk of Admission or ED visit.

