At present, evidence-based, client-directed strategies such as patient reminders and recalls, one-on-one patient education, and patient navigation, are the basis for behavioral interventions to increase cervical cancer screening rates. Patient reminders inform patients that they are due for screening, while recalls inform them they are past-due. Patient navigation, a barrier-focused intervention, involves individual interactions with patients to address individual-level barriers along the continuum of care through to a specific endpoint (e.g., cancer screening). These existing client-directed strategies alone are often unable to resolve many of the barriers faced by screening non-attendees. Of note, we recently found that as many as 10% of women attending safety net community health centers in Harris County reported never having had a Pap test despite having visited those clinics an average of nearly four times in the past year. This observation suggests that current standard of care cervical cancer screening may be simply unacceptable or unfeasible for many women.

Testing self-collected cervicovaginal samples for HR-HPV may be an effective strategy to overcome the multiple barriers that hinder clinic-based screening. Testing for HR-HPV has been shown to be equally or more sensitive than liquid-based cytology for detecting invasive cervical cancer and high-grade lesions. Reflecting its sensitivity, HR-HPV testing using provider-collected samples is now recommended by the US Food and Drug Administration (FDA) as an alternative to Pap test screening. Recently, it has become the primary screening tool in The Netherlands and Australia and is being considered as such in several other countries. Substantial evidence indicates that samples can be collected by providers or by women themselves, with similar sensitivity for detecting HR-HPV nucleic acid. Numerous studies, including our own, have demonstrated high acceptability for a self-sampling modality. In our own research, a sizeable

proportion of women indicated a preference to utilize self-collected samples rather than undergo a pelvic examination by a healthcare provider and considered self-sampling more convenient and less stressful than clinic-based screening. These and other data thus pave an exciting path for the expansion of primary screening from clinical settings into women's homes through mailed self-sample HPV testing kits.

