3 STUDY METHODS

3.1 Study Methods

Eligible women will be identified monthly through a query of the EMR database. Data will be extracted and transferred to OnCore (Forte Research Systems, Madison, WI) for randomization, storage, and data management. A computer-generated permuted block randomization scheme will be used to randomly assign individuals to the three trial arms with a 1:1:1 ratio using participants' medical record number. Randomized women will receive a study-specific identification number. Randomized women will be contacted by telephone. Those who are not reached will be contacted on 3 different days at 3 different times before being classified as unreachable. Unreachable participants will be replaced by randomly-selecting additional eligible women until the target sample size is met. Women who hang up the telephone before the scripted message is delivered will receive a second call within 10-30 minutes. Those who do not hear the full message on the second attempt will be categorized as refusers.

The 3 arms of the RCT are: Arm 1: Telephone recall (control). Participants will receive a scripted telephone recall from a trained patient navigator (PN) on behalf of Harris Health. Arm 2: Telephone recall with mailed HPV self-sampling kit (intervention). Participants in this arm will receive a scripted telephone recall from a PN on behalf of Harris Health and receive a mailed HPV self-sampling kit with a pre-paid return envelope.

Arm 3: Telephone recall with mailed HPV self-sampling kit and patient navigation (intervention plus). Participants in this arm will receive the same scripted telephone recall and mailed self-sampling kit as in Arm 2. Within 3-5 days of the kit's mail-out, participants will receive a telephone call from the PN.

Procedures for the three arms of the RCT are as follows:

Arm 1: Telephone recall (control). Participants will receive a scripted telephone recall from a trained patient navigator (PN) on behalf of Harris Health. PNs will let the patient know of the telehealth options available to Harris Health patients during the COVID-19 pandemic. Patients will be given the contact information for the call center that can walk them through the steps of accessing telehealth. PNs will also inform participants that their records indicate that they are overdue for a Pap test and that primary care, including well woman exams and Pap testing is still important during the pandemic.

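### The primary arm comparison uses no baseline covariates, although six are planned for the same outcome in a sub-aim; prespecified adjustment would give a modest gain in precision

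*Combined protocol and SAP*

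**What the plan says.** All references are to the combined protocol and SAP.

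- **Primary comparison, section 3.4.** "Bivariable tables and Pearson's χ^2 tests will be used to compare the proportion of primary screening participation by study arm", together with absolute differences. For the effect estimate, "Log binomial regression will be used to calculate the relative risks of primary screening participation and corresponding 95% confidence intervals (CIs"). No covariate is named for either.
- **Baseline characteristics, section 3.4, sub-aim 3.** "Characteristics of interest include age, race/ethnicity, months since last Pap test, health plan type, number of healthcare encounters in the past 12 months"; length of enrolment with the health system completes the list of six. They are first screened singly against participation: "Associations with $p<0.10$ will be used to determine candidate variables for subsequent multivariable" models. Then: "Multivariable log binomial regression models will be built to assess the independent association between screening participation and participant characteristics after adjusting for relevant covariates". These adjusted risk ratios describe who gets screened. They are not an adjusted arm contrast.
- **Randomisation, section 3.1.** "A computer-generated permuted block randomization scheme will be used to randomly assign individuals to the three trial arms with a 1:1:1 ratio". No stratification factor is named.
- **Data source, section 3.1.** "Data will be extracted and transferred to OnCore (Forte Research Systems, Madison, WI) for randomization, storage, and data management". The extracted fields are not listed.
- **Sample size, section 4.** 756 women per arm, for a difference of at least 6 points between Arms 2 and 3. No base rate, alpha or power is stated for this calculation.

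**The concern.** The plan intends to relate six baseline variables to screening participation, yet neither the allocation nor the primary comparison uses any of them. When baseline variables predict a binary outcome, a prespecified adjusted estimate of the marginal risk difference or risk ratio has a smaller standard error. It also accounts for chance imbalance between arms in those variables. The Arm 3 v Arm 2 contrast, on which the trial is sized, would benefit.

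At stake is some precision on that contrast, obtainable from record data the trial already plans to analyse. There is also a prespecification benefit. With no covariate list fixed for the arm comparison, any adjusted arm estimate reported later would rest on choices made after the data were seen.

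**Working it through.** **Inputs from the documents.** 756 per arm and a 6-point difference between Arms 2 and 3 (section 4); kit return of 10-39% in earlier trials (section 1.2), used here as a range for the Arm 2 rate.

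**Assumed, because not stated.** Arm 2 rate, two-sided alpha 0.05, and R², the share of outcome variance explained by the covariates.

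**Step 1: the plan's figure.** 756 cannot be derived from stated inputs alone. For 18% v 24%, two-sided alpha 0.05 and 80% power:

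n = [1.96·√(2·0.21·0.79) + 0.8416·√(0.18·0.82 + 0.24·0.76)]² / 0.06² = 722.2, so 723.

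With continuity correction, n/4·[1 + √(1 + 4/(n·0.06))]² = 755.2, so 756. The match is exact but not unique: 19% v 25% without correction gives 748, and 12% v 18% at 90% power gives 743. I use 18% v 24% as a working assumption.

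**Step 2: unadjusted power with 756 per arm (no continuity correction).**

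- s0 = √(2·0.21·0.79/756) = 0.02095
- s1 = √((0.18·0.82 + 0.24·0.76)/756) = 0.02089
- Power = Φ((0.06 − 1.96·0.02095)/0.02089) = Φ(0.907) = 81.8%
- 95% CI half-width = 1.96·0.02089 = 4.09 points

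**Step 3: gain from adjustment.** The standard error is multiplied by √(1−R²), which is equivalent to an effective n of 756/(1−R²). The fourth column, 756·(1−R²), is the adjusted n per arm that matches the unadjusted precision.

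| R² | SE ratio | Effective n per arm | n for same precision | CI half-width (points) | Power, 18% v 24% |
|---|---|---|---|---|---|
| 0 | 1 | 756 | 756 | 4.09 | 81.8% |
| 0.01 | 0.995 | 764 | 748 | 4.07 | 82.1% |
| 0.02 | 0.990 | 771 | 741 | 4.05 | 82.5% |
| 0.05 | 0.975 | 796 | 718 | 3.99 | 83.7% |
| 0.10 | 0.949 | 840 | 680 | 3.88 | 85.6% |

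**Step 4: other base rates.** Power unadjusted, then adjusted at R² = 0.01 to 0.10:

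- 10% v 16%: 93.5%, then 93.7% to 95.6%
- 30% v 36%: 69.9%, then 70.3% to 74.4%
- 39% v 45%: 65.7%, then 66.1% to 70.3%

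**Step 5: simulation check.** Logistic standardisation for the risk difference, 756 per arm, base rates 15%, 21% and 30%, one prognostic score plus five noise covariates, 3,000 runs per setting. The ratio of adjusted to unadjusted standard error was:

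- 1.002-1.003 with no prognostic value
- 0.988-0.997 at an odds ratio of 1.35 per SD of the score
- 0.975-0.982 at 1.65
- 0.943-0.963 at 2.23

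This agrees with the formula: a small gain for weak predictors, and negligible loss when there is nothing to gain.

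**The case against.** The strongest reply is that nothing is wrong with the plan. Women are individually randomised 1:1:1, no stratification factor has to be carried into the analysis, and the unadjusted test, difference and relative risk are all valid. Chance imbalance is already reflected in the confidence interval. This stands. A reader might infer that the primary estimate is biased or misspecified; the documents do not support that for the 1:1:1 trial.

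A reader might also infer that known prognostic variables, already held for every woman, are being wasted. That goes beyond the text in three ways.

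- **Prognostic value.** Section 3.4 calls the six characteristics of interest and screens them at p<0.10, so their predictive value is what sub-aim 3 sets out to learn. Section 1.2 does report national screening participation of 63.7% in Asian/Asian American women against 79.5% in non-Hispanic White women. It gives no strength for any of the six in this overdue population. Eligibility already requires women to be overdue, with visits and coverage, which narrows the spread of several of them.
- **Availability.** The eligibility criteria in section 4.1 imply that age, Pap history, coverage and visit history exist in the record. Completeness of race/ethnicity and time enrolled is not documented.
- **Cost.** Adjustment is not entirely free. Months since last Pap is undefined for women never screened. Section 4.1 admits them, and section 1.2 reports that "as many as 10% of women attending safety net community health centers in Harris County reported never having had a Pap test". A model without a rule for these women would drop them and damage the intent-to-screen analysis. An adjusted log binomial model may also fail to converge.

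These objections limit the size and certainty of the gain. They do not remove the case for prespecifying the adjustment.

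A separate matter is the supplement cohort, allocated 120/60/60. If pooled with the main trial it would form 13.7% of Arm 1 (120/876) and 7.4% of each of Arms 2 and 3 (60/816). How the cohorts are combined needs its own statement; the Arm 3 v Arm 2 contrast is not affected.

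**Conclusion.** The point holds as an efficiency improvement. No covariate-adjusted arm comparison is prespecified, although the plan will relate six baseline characteristics to the same outcome.

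At an assumed 18% v 24%, power rises by under 1 point if the covariates explain 1-2% of outcome variance, by about 2 points at 5% and by about 4 points at 10%. The standard error falls by 0.5% to 5.1% over that range. At an assumed 30% v 36% the corresponding rise is from 69.9% to between 70.3% and 74.4%. With non-prognostic covariates there is essentially no gain.

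The omission is plain from section 3.4. The size of the gain is not: it rests on assumed base rates, alpha and R², none of which the documents give for this contrast. A large or guaranteed loss of precision cannot be claimed.

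**What to change.** In section 3.4, make the primary estimate a standardised (marginal) risk difference and risk ratio. Derive both from a logistic model containing arm and the six named baseline characteristics, with robust or delta-method standard errors.

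- Enter the fixed list whole. The p<0.10 screening of sub-aim 3 should play no part in the arm comparison.
- Code time since last Pap in categories, one of which is never screened or no record.
- Use a missing category for any incomplete record field, so that no woman leaves the intent-to-screen analysis for lack of a covariate.
- State the functional form of each variable before outcome data are examined.
- Keep the unadjusted chi-square and log binomial results as supportive.

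The cost is SAP wording and analysis code, the work of fixing functional forms in advance, and slightly more complex reporting. No data are needed beyond the record variables already planned for sub-aim 3.
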